6.2.1.1 Additional follow-up for hepatic toxicities

Hepatic toxicity monitoring includes the following LFTs: albumin, ALT, AST, total bilirubin (fractionated if total bilirubin $> 2 \times$ ULN), alkaline phosphatase (fractionated if alkaline phosphatase is grade 2 or higher) and GGT. For patients with Gilbert’s Syndrome: total and direct bilirubin must be monitored, intensified monitoring applies to changes in direct bilirubin only.

Close observation is recommended in case of AST, ALT, and/or bilirubin increase requiring dose interruption, which involves:

[figure not shown]
- Repeating liver enzyme and serum bilirubin tests **two or three times weekly**. Frequency of re-testing can decrease to once a week or less if abnormalities stabilize or return to normal values.
- Obtaining a more detailed history of current symptoms.
- Obtaining a more detailed history of prior and/or concurrent diseases.
- Obtaining a history of concomitant drug use (including non-prescription medications, herbal and dietary supplements), alcohol use, recreational drug use, and special diets.
- Ruling out acute viral hepatitis types A, B, C, D, and E; hepatotropic virus infections (Cytomegalovirus (CMV), Epstein Barr Virus (EBV) or Herpes Simplex Virus (HSV); autoimmune or alcoholic hepatitis; non-alcoholic steatohepatitis (NASH); hypoxic/ischemic hepatopathy; and biliary tract disease.
- Obtaining a history of exposure to environmental chemical agents.
- Obtaining additional tests to evaluate liver function, as appropriate (e.g., INR, direct bilirubin).
- Considering gastroenterology or hepatology consultations.

Assessing cardiovascular dysfunction or impaired liver oxygenation, including hypotension or right heart failure as possible etiologies for liver dysfunction.

6.2.1.2 Additional follow-up for QTc prolongation

Table 6-5 Study drug dose adjustment and management recommendation

Grade	Dose Modification
For All Grades	
 • Check the quality of the ECG. • Perform analysis of serum electrolytes (K⁺, Ca⁺⁺, Phos, Mg⁺⁺). If outside of the normal range, interrupt study drug administration, correct with supplements or appropriate therapy as soon as possible, and repeat electrolytes until documented as normal. • Review concomitant medication usage for the potential to inhibit • CYP3A4 and/or to prolong the QT interval.

[figure not shown]
Grade	Dose Modification
	
 Check compliance with correct dose and administration of study drug
1 QTc 450-480 ms	No dose adjustment required.
2 QTc 481-500 ms	
Interrupt study drug
 
Perform a repeat ECG one hour after the first QTcF of ≥ 481 ms.
 
If QTcF ≤ 481 ms, restart study drug at the same dose. No dose adjustment required for first occurrence.
 
If QTcF remains ≥ 481 ms, repeat ECG as clinically indicated until the QTcF returns to < 481 ms. restart study drug at the same dose. No dose adjustment required for first occurrence.
 
If QTcF ≥ 481 ms recurs, study drug should be reduced by 1 dose level. Refer to Table 6-2 for dosing schedule.
 
Repeat ECGs 7 days and 14 days after dose resumption (then as clinically indicated) for any patients who had therapy interrupted due to QTcF ≥ 481 ms

3 QTc ≥ 501 ms on at least two separate ECGs	
Interrupt study drug. Transmit ECG immediately and confirm prolongation/abnormalities with central assessment.
 
Perform a repeat ECG one hour after the first QTcF of > 501 ms.
 
If QTcF remains ≥ 501 ms, consult with a cardiologist (or qualified specialist) and repeat cardiac monitoring as indicated, until the QTcF returns to < 481 ms.
 
If QTcF returns to < 481 ms, study drug will be reduced by 1 dose level. Refer to Table 6-2 for dosing schedule.
 
Repeat ECGs 7 days and 14 days after dose resumption (then as clinically indicated) for any patients who had therapy interrupted due to QTcF ≥ 501 ms
 
If QTcF of ≥ 501 ms recurs, discontinue study drug

4 [QT/QTc ≥ 501 or > 60 ms change from baseline] and [Torsades de pointes or polymorphic ventricular tachycardia, or signs/symptoms of serious arrhythmia]	
 Discontinue study drug. 
 Obtain local cardiologist consultation. Perform a repeat ECG one hour after the first QTcF of ≥ 501 ms. If QTcF remains ≥ 501 ms, repeat ECG as clinically indicated, but at least once a day until the QTcF returns to < 501 ms.

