6.2 Dose modifications

6.2.1 Dose modification and dose delay

For patients who do not tolerate the protocol-specified dosing schedule, dose adjustments are permitted in order to allow the patient to continue the study drug. These changes must be recorded on the Dosage Administration Record eCRF. For patients undergoing a dose delay or reduction mid-cycle, upon restarting LEE011 during that cycle the, dosing should resume per the original cycle schedule. The planned 7-day break should begin on the originally planned date regardless of mid-cycle interruptions. Day 1 of subsequent cycles may be delayed if necessary to allow for toxicity resolution. If the study drug is delayed for more than 21 days due to drug toxicity, then study drug should be discontinued.

Severe or intolerable AEs may require dose reduction and/or interruption of study drug. Refer to Table 6-2 for guidance.

Table 6-2 Dose adjustments

Dose level	Daily dose	Frequency
*-2	200 mg	Daily (21 days), followed by one week break
*-1	400 mg	Daily (21 days), followed by one week break
1 (starting dose)	600 mg	Daily (21 days), followed by one week break

*Dose level-1 and -2 represent treatment doses for patients requiring a dose reduction from the starting dose level. No dose reduction below dose level -2 is permitted for this study.

[REDACTED]

Recommendations for dose reduction, interruption or discontinuation of study drug in the management of AEs are summarized in [Table 6-3](#). Clinical judgment of the treating physician and an individualized risk/benefit assessment should guide the management plan for each patient. A maximum of two study drug dose reductions (minimum dose is 200 mg) is allowed before study drug must be discontinued. Once a dose reduction has occurred, the dose level may not be re-escalated until the adverse event resolves to grade 1 and dose change has been authorized by the Novartis team.

Table 6-3 Study drug dose adjustment and management recommendation for hematological adverse reactions

[figure not shown]
Toxicity/Grade	Dose Adjustment and Management Recommendations
Thrombocytopenia	
Grade 1 ($\geq 75 \times 10^9/L$)	No dose adjustment required.
Grade 2 ($\geq 50 \times 10^9/L - < 75 \times 10^9/L$)	Dose interruption until recovery to grade ≤ 1 . Re-initiate study drug at the same dose.

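### Protocol Table 6-5, Grade 2: a repeat QTcF of exactly 481 ms meets both the restart rule and the continue-holding rule; secondarily, the Table 7-4 footnotes disagree on who has Day 1 ECGs after cycle 6

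*Protocol*

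**What the plan says.** **Table 6-5 (Protocol 6.2.1.2).** Grade 1 is 450 to 480 ms and needs no dose change. Grade 2 is 481 to 500 ms: drug is interrupted, and the instruction is "Perform a repeat ECG one hour after the first QTcF of ≥ 481 ms". Two lines deal with the result of the repeat:

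- Restart: "If QTcF ≤ 481 ms, restart study drug at the same dose".
- Continue holding: "If QTcF remains ≥ 481 ms, repeat ECG as clinically indicated until the QTcF returns to" a value below 481 ms, after which drug restarts at the same dose.

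For a later episode the row says "If QTcF ≥ 481 ms recurs, study drug should be reduced by 1 dose level".

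**Table 7-4 (Protocol 7.2.2.6.1).** After the named visits up to cycle 6, one row gives a Day 1 pre-dose ECG in all remaining cycles. Its footnote a confines the row to patients who had a QTcF of 481 ms or more before cycle 7. Two further rows cover cycle 9 and every third cycle after it, pre-dose and 2 h post-dose. Their footnote b asks for a pre-dose ECG on Day 1 in each cycle and names no patient group. Table 7-1 marks an ECG on Day 1 of subsequent cycles without restriction and refers to Section 7.2.2.6.1.

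**The concern.** The Grade 2 row sets the threshold for putting a patient back on drug after a QTc hold. At 481 ms it gives two answers. Reading the lines in order does not resolve this, because the first line restarts drug in a patient who still meets the definition of the grade that stopped it. QTcF prolongation is the toxicity that helped set the dose: Protocol 2.3 gives a lower risk of it as one reason for choosing 600 mg over the maximum tolerated dose of 900 mg. The restart rule for that toxicity should give one answer.

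The Table 7-4 point is about monitoring. For a patient without early prolongation, the two footnotes lead to different numbers of scheduled ECGs from cycle 7 on, and a site cannot tell from the table alone which applies.

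**Working it through.** The plan gives no figure to reproduce here. The check is one of logic and counting.

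**1. The two Grade 2 lines, by value of the repeat QTcF**

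| Repeat QTcF | Restart line (≤ 481) | Hold line (≥ 481) | Restart line if changed to < 481 |
|---|---|---|---|
| 480 ms | met | not met | met |
| 481 ms | met | met | not met |
| 482 ms | not met | met | not met |

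Among whole values from 478 to 484 ms, only 481 ms meets both lines. With the restart line at < 481 ms, each value meets exactly one line, with no overlap and no gap.

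**2. Which sign is out of step**

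Other statements in Table 6-5 that place the cut between 480 and 481 ms:

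- Grade 1 range: ends at 480
- Grade 2 range: starts at 481
- Grade 2 repeat trigger: ≥ 481
- Grade 2 continued hold: ≥ 481
- Grade 2 recovery: < 481
- Grade 2 recurrence: ≥ 481
- Grade 2 follow-up ECGs after resumption: ≥ 481
- Grade 3 monitoring: until < 481
- Grade 3 resumption: < 481

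That is nine statements treating 481 ms as prolonged. The restart line is the only one that does not.

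**3. Consequence at 481 ms on a first occurrence**

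Both lines lead to resumption at the same dose. Only the time of restart differs: after the one-hour repeat, or after a later reading below 481 ms.

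**4. Table 7-4, Day 1 pre-dose ECGs in cycles 7 to 15**

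- Patient with QTcF ≥ 481 ms before cycle 7: both footnotes give all nine cycles, so there is no conflict.
- Patient without it, if footnote a governs: cycles 9, 12 and 15, which is 3.
- Same patient, if footnote b governs: all 9.
- Difference: 9 − 3 = 6, in cycles 7, 8, 10, 11, 13 and 14. If footnote b is taken to start only at cycle 9, cycles 7 and 8 drop out and 4 remain.

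Three nominal cycles are 3 × 28 = 84 days. In that time the patient has 1 scheduled pre-dose ECG under footnote a and 3 under footnote b. The longest nominal interval between scheduled ECG days is 84 or 28 days.

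**5. Reach**

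The Amendment 3 status note counts 4 patients on treatment on 18-Aug-2017. For patients without early prolongation, the unrestricted schedule means 3 − 1 = 2 more pre-dose ECGs per 84 days than the restricted one, so at most 2 × 4 = 8 for all four.

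**The case against.** **The sign may be a reading error.** The text was read from PDF by a program, and the nine-to-one count fits a misread sign as well as a sponsor's slip. The neutrophil, platelet and hemoglobin cut-offs are strict in the protocol summary and non-strict in Section 5.3, and it cannot be told from here whether the source or the reading is at fault. Against this, the same Grade 2 cell shows all three signs (≤, <, ≥) as distinct. What stands is that the page must be checked before anything is changed.

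**The effect is almost nil.** Largely right. The next line shows what was meant, Section 6.2.1 says "Clinical judgment of the treating physician and an individualized risk/benefit assessment should guide the management plan for each patient", and ECGs follow 7 and 14 days after resumption in any case. This argues for low priority, not for leaving a contradictory dosing threshold in place.

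**A reader might infer that the dose differs between the two lines.** On a first occurrence it does not. One could argue that a patient restarted at 481 ms who reads 481 ms again a week later would be counted as a recurrence and have the dose reduced. The table does not say how such a reading is counted, so the point does not rest on it.

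**A reader might infer that Table 7-4 leaves patients 84 days between ECGs.** That follows only if a site applies footnote a against both footnote b and Table 7-1, and Section 7.1 allows extra assessments when clinically indicated.

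**A reader might infer the reverse, that a restricted schedule was intended.** A universal footnote b leaves footnote a with nothing to do, and the Amendment 2 rationale describes continued monitoring after prolongation. That rationale is an amendment log and uses a different cut-off (before Cycle 9 Day 1), so it does not settle the intent. Section 7.2.2.6.1 also has redacted text between the baseline-ECG instructions and Table 7-4. That text may contain the answer, and its absence here is not a gap in the plan.

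**Conclusion.** The main point holds as a minor patient-safety correction. As the text reads, a one-hour repeat QTcF of exactly 481 ms is told both to restart and to keep holding, and the rest of the Grade 1 to 3 rows show that holding was meant. The size is one whole-millisecond value and, on a first occurrence, a difference in restart time only. This assumes that the sign on the original page is the one read here and that QTcF is recorded in whole milliseconds, as the grade ranges imply.

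The secondary point holds as a clarification. The footnotes of Table 7-4 conflict for patients without a QTcF of 481 ms or more before cycle 7. The visible text leans towards all patients, subject to what the redacted part says.

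Neither point touches any analysis: SAP Section 4 drops the PFS analysis and all ECG tables and listings. At most 4 patients were still on treatment at the last status date, 3 of them blinded and so possibly on placebo. Transfer to the rollover study, allowed in Section 7.1.3, would reduce that number.

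**What to change.** **Table 6-5, Grade 2.** Check the sign on the original page. If it is ≤, change the restart condition to QTcF < 481 ms. This costs one character, and no other line of the row needs to change.

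**Table 7-4.** Remove footnote a's restriction, so that the row for all other cycles applies to every patient, in line with footnote b and Table 7-1. If the sponsor confirms that a restricted schedule was meant, state the patient group once and word footnote b and Table 7-1 to match. Compared with a site now following footnote a, the unrestricted schedule adds at most 2 pre-dose ECGs per patient per 84 days. Compared with a site following footnote b, it adds none.

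### Table 6-5: the grade 3 QTc heading requires two ECGs but its row text acts on the first, so an unconfirmed reading above 501 ms has no settled dose outcome

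*Protocol*

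**What the plan says.** Table 6-5 in protocol section 6.2.1.2 has four graded rows. Their headings are:

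- "1 QTc 450-480 ms"
- "2 QTc 481-500 ms"
- "3 QTc ≥ 501 ms on at least two separate ECGs"
- "4 [QT/QTc ≥ 501 or > 60 ms change from baseline] and [Torsades de pointes or polymorphic ventricular tachycardia, or signs/symptoms of serious arrhythmia", the last of these combining a QT criterion with an arrhythmia criterion.

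The grade 3 text interrupts the drug, sends the ECG for central confirmation, and continues: "Perform a repeat ECG one hour after the first QTcF of > 501 ms". If the value stays at 501 ms or more, it calls for a cardiology consultation and continued monitoring until QTcF is below 481 ms. It then states: "If QTcF returns to < 481 ms, study drug will be reduced by 1 dose level". The row ends with permanent discontinuation if a value of 501 ms or more comes back.

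The grade 2 text also interrupts the drug and says: "Perform a repeat ECG one hour after the first QTcF of ≥ 481 ms". If the repeat is low: "If QTcF ≤ 481 ms, restart study drug at the same dose. No dose adjustment required for first occurrence".

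**The concern.** A heading tells the site which row applies, and the text tells it what to do. In the grade 3 row the two use different conditions. The heading cannot be met until a second ECG has been read, while the text interrupts the drug and orders that second ECG on the strength of the first. The row therefore anticipates that a first high reading may not be confirmed, but never says in terms what follows when it is not.

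Lower QTcF risk is among the reasons that protocol section 2.3 gives for developing 600 mg rather than the 900 mg maximum tolerated dose, so the QTcF rule is a central safety rule here. At stake are the dose at which a patient restarts and whether a later high reading ends treatment.

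**Working it through.** No sample size, power or error rate is involved. The check is to set headings and texts side by side and trace pairs of readings (first ECG, one-hour repeat) through them, assuming no torsades, polymorphic ventricular tachycardia or signs of serious arrhythmia. With any of these, the grade 4 row applies to a single reading of 501 ms or more.

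**Step 1: headings.** Grade 1 covers 450-480 ms, grade 2 covers 481-500 ms, and grade 3 needs 501 ms or more twice. Take first readings of 501 to 560 ms (60 integer values) and repeats of 400 to 500 ms (101 values): 60 × 101 = 6,060 unconfirmed pairs. None matches a heading. This is a completeness check on the rules and says nothing about how often such pairs occur.

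The repeat taken alone may fall under grade 1 or grade 2. But the table does not say that the repeat replaces the first reading, and the reading that caused the interruption still has no row.

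**Step 2: grade 3 text, read from the first ECG.**

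| First (ms) | Repeat (ms) | Heading met | Grade 3 text |
|---|---|---|---|
| 505 | 470 | none | reduce one level |
| 505 | 490 | none | no instruction at one hour; reduce one level once below 481 |
| 505 | 505 | grade 3 | cardiology input and monitoring; reduce one level once below 481 |
| 501 | 470 | none | repeat-ECG trigger (above 501) not met |
| 501 | 501 | grade 3 | heading met, repeat-ECG trigger not met |

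For 505 then 470 ms, heading and text disagree. The heading leaves the patient outside the row, and the text lowers the dose.

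For 505 then 490 ms, only the interim instruction is missing. The clause on falling below 481 ms is not tied to the one-hour ECG and still applies later.

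At exactly 501 ms, the heading (501 or more) and the repeat trigger (above 501) differ from each other.

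**Step 3: the heading taken as governing.** If the dose reduction applies only to confirmed cases, or only after a value that stayed at 501 ms or more, then 505 followed by 470 ms leaves a patient whose drug was interrupted for the repeat ECG, with no stated rule for restarting.

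**Step 4: later episodes.** The row discontinues the drug when a value of 501 ms or more comes back. It does not say whether an unconfirmed first reading counts as the first episode. If it counts, a later such reading means discontinuation. If it does not, the later reading is handled as a first one.

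**Step 5: dose size.** Table 6-2 puts one level down from the starting dose at 400 mg: (600 − 400) / 600 = 33%.

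**The case against.** The strongest reply is that the row can be read in sequence. The text is staged from the first reading: interrupt, confirm centrally, repeat at one hour, act once below 481 ms. On that view a first value above 501 ms enters the row at once, the dose is reduced, and the heading is loose drafting. This is a natural reading, and if the sponsor means it the correction is small. But it sets aside the heading's requirement for two ECGs, and nothing in the table tells a site to do that.

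Safeguards also exist. Table 6-5 asks sites to check ECG quality at all grades, section 7.2.2.6.1 provides for central review of tracings, and section 6.2.1 leaves room for clinical judgment. These help to sort a true prolongation from an artefact, but none states a dose outcome for an unconfirmed reading.

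A reader might go further and infer that the table gives opposite orders, because the grade 2 trigger starts at 481 ms with no upper limit and leads to restart at the same dose. The documents do not establish that. The grade 2 row is headed 481-500 ms, and its text reaches a first reading of 505 ms only if detached from that heading. Detached in this way, it would also catch a confirmed pair of 505 and 505 ms, so it cannot be used to call the confirmed case clean and the unconfirmed one contradictory. The open-ended trigger adds to the ambiguity and no more.

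Finally, the reach is limited. Enrollment stopped at 10 patients, and 4 were on treatment at 18-Aug-2017. What stands is that they were still being dosed, Amendment 3 allows placebo patients to cross over to LEE011, and Table 7-1 schedules ECGs in the crossover cycles.

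**Conclusion.** The grade 3 heading and row text of Table 6-5 contradict each other. For a patient without the grade 4 arrhythmia criteria, a first QTcF above 501 ms that is not confirmed at one hour falls under no heading. The row text read from the first ECG leads to a one-level reduction (33% from the starting dose). The heading read strictly leaves an interrupted drug without a restart rule. Three smaller gaps go with this: no interim instruction for a repeat of 481-500 ms, a mismatch at exactly 501 ms, and no statement on whether an unconfirmed reading counts toward discontinuation.

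The case rests on patient safety and consistent dosing. A reader might also infer damage to the dose-change data, but SAP section 4 drops the tolerability summaries and the listing of reasons for dose interruption, reduction and change. Adverse event outputs by dose adjustment remain (SAP section 3.6.1), which is too little to carry that argument.

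The conclusion assumes that no blacked-out text settles the matter. Part of section 7.2.2.6.1 is redacted; Table 6-5 itself is not. The documents give no frequency for such readings, so none is claimed.

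**What to change.** The sponsor should reconcile the grade 2 and grade 3 headings and thresholds in Table 6-5 with their row texts, so that a first reading of 501 ms or more followed by a repeat below 481, of 481-500, or of 501 ms or more leads to exactly one stated outcome each. The same threshold should be used in the grade 3 heading and its repeat trigger. The table should also say whether an unconfirmed reading counts as a first episode for the discontinuation rule. Which dose outcome applies is a clinical decision for the sponsor, and this review takes no position on it.

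The cost is a wording change in two rows of one table, made through a protocol amendment. No additional ECGs are needed.

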6.2.1.3 Guidance for all other adverse reactions

Consider performing an analysis of serum potassium, calcium, phosphorus, and magnesium for all adverse reactions, if indicated. If electrolyte values are below the lower limit of normal, interrupt study drug administration, correct electrolytes with supplements as soon as possible, and repeat electrolyte testing until documented normalization of the electrolytes.

Table 6-6 Study drug dose adjustment and management recommendation for all other adverse reactions

Grade	Dose Adjustment and Management Recommendations
1	No dose adjustment recommended. Initiate appropriate medical therapy and monitor.
2	
Dose interruption until recovery to grade ≤ 1. Initiate appropriate medical therapy and monitor. Re-initiate study drug at the same dose.
 
If the same toxicity recurs at grade 2, interrupt study drug until recovery to grade ≤ 1. Re-initiate study drug at the next lower dose level.

3	
Dose interruption until recovery to grade ≤ 1. Initiate appropriate medical therapy and monitor. Re-initiate study drug at the next lower dose level.
 
If toxicity recurs at grade 2: temporary dose interruption until recovery to grade ≤ 1 and reduce study drug dose the next lower dose level.
 
If toxicity recurs at grade 3, discontinue study drug

Grade	Dose Adjustment and Management Recommendations
4	Discontinue study drug and treat with appropriate medical therapy.

